7.5 ANALYSIS VISIT WINDOW

In general, all efficacy and safety data will be summarized by study week based on the schedule of events in [Table 1](#). The visits indicated on the eCRF (Baseline Day 1, Week 12, Week 24, Week 36, Week 48, Week 60, Week 72, Week 84/EOS, and 2 Week Follow-up) will be used as the analysis visits for analysis of most safety parameters including vital signs, laboratory examinations, and ECGs.

After mapping the data to the analysis visits as shown, the following rules will apply unless other handling is specified for a particular analysis.

- If multiple records are available within a single analysis visit window, the record closest to the planned assessment day will be selected for analysis.
- If two records are equidistant from the target day, then the later record will be selected.
- If a subject has no record in an analysis window, the subject's data will be considered missing at that time-point.

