7 GENERAL ASPECTS FOR STATISTICAL ANALYSIS

7.1 GENERAL METHODS

Statistical methodology and analyses are in accordance with the principles outlined by the International Conference on Harmonisation (ICH) E9 guidelines^[1].

Patient listings of all data represented in the electronic case report form (eCRF) will be provided. Measurements from patients excluded from the predefined analysis populations or extra measurements (such as unscheduled or repeat assessments) will not be included in summary tables unless specified otherwise, but will be included in the patient listings. In general, the patient listings will be sorted by treatment group,

1003157

Lexicon Pharmaceuticals, Inc.

LX1606.302

Final V1.0

Statistical Analysis Plan

patient number, and assessment date (and time), if applicable. For most summary statistics, data will be analyzed and displayed by the order of the treatment groups and overall, where treatment groups correspond to how patients were dosed on Day 1 of this study.

Unless otherwise specified, continuous/quantitative variables will be summarized using descriptive statistics, which will include the number of patients with data to be summarized (n), mean, standard deviation (SD), median, minimum, and maximum. The same number of decimal places as in the raw data will be presented when reporting the minimum and maximum, 1 more decimal place than in the raw data will be presented when reporting the mean and median, and 2 more decimal places than in the raw data will be presented when reporting the SD.

All categorical/qualitative data will be presented using frequency counts and percentages. The total number of patients in the treatment group overall (N) will be used as the denominator for percentage calculations, unless stated otherwise in the table shell. All percentages will be presented as 1 decimal point, unless otherwise specified. Percentages equal to 100 will be presented as 100%, and percentages will not be presented for zero frequencies.

All statistical tests will be 2-sided and have an associated α -level = 0.05 unless mentioned otherwise. Confidence limits (CLs) will be 2-sided and calculated with a 95% confidence coefficient.

All statistical analyses will be done using SAS statistical software version 9.3 or higher.

In the case of multiple or repeat assessments at a scheduled visit, the latest value at the visit will be used for summarization and analyses.

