7.2.6 End of Study

The end of study (EOS) is defined as date of early termination or the date of completion of treatment for enrolled patients. It will be obtained from the eCRF. The EOS value is defined as the last non-missing measurement or assessment on or before the EOS.

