9.5 ECG

Electrocardiograms (12-lead ECGs) will be performed as specified in [Table 1](#). The following ECG parameters will be recorded: heart rate (bpm), RR interval (msecs), PR interval (msecs), QRS interval (msecs), QT interval (msecs), and corrected QT (QTc) intervals (msecs). QT will be corrected for heart rate using Fridericia’s (QTcF) interval.

For each ECG parameter, the observed value and change from Baseline value will be summarized using descriptive statistics by study visit and treatment group for all patients in the safety population.

In addition, count and percentage of patients with outlying QTcF values (i.e., value >450, >480 or >500 msec, increase from Baseline value of >30 or >60 msec) based on ICH Guidance E14^[4] will be presented by study visit and treatment group.

All ECG data will be included in patient listings.

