- Where the SDAEP eCRF includes both the first dose and last dose dates, the patient's duration of open label treatment exposure will be calculated using these dates. If the page also includes study drug compliance information, these patients will also be included in the reporting of study drug compliance.
- Any patient without a last dose date will have their duration of exposure estimated by using the date of the last recorded visit in the eCRF (scheduled or unscheduled), up to and including the week 48 visit (ie, excluding Follow Up visits). The time on study drug will be estimated for these patients, but no estimation will be performed that includes study drug compliance, dose, or amount of drug received during the study.
- A review has been completed of all adverse events for all patients in the open-label extension periods to ascertain if any patients may have been identified on the AE eCRF as having discontinued the study, discontinued study drug, or interrupted study drug due to an adverse event, but do not have a last dose date on the SDAEP eCRF. Within the data extracted for these studies at this time, no such AEs exist.

Signed: [redacted]
[redacted] MD
[redacted] Clinical Operations

NOTE TO FILE

To: LX1606-1.302-CS Trial Master File (TMF)

From: [REDACTED] of Biostatistics and Data Management
[REDACTED] of Biostatistics

Re: Study LX1606-1.302-CS: Handling of the Week 84/End of Study (EOS) Efficacy Data in the Statistical Analysis for Patients who Discontinued from the Study Prior to Week 84

Date: November 23, 2015

-
- I. **Incident/Finding(s):** According to Section 7.5 of the Final Statistical Analysis Plan (dated 24Nov2014), efficacy data are to be summarized by study week based on the study's schedule of events (in Table 1 of the SAP; also in Appendix A of the protocol). However, the efficacy data recorded at Week 84/EOS include not only efficacy data assessed at the Week 84 visit for patients who completed the study, but also efficacy data assessed at the last visit (ie, EOS visit) for patients discontinued from the study prior to Week 84. This Note-to-File (NTF) describes how the EOS visit for the latter patients will be mapped, for purposes of tabular summaries and statistical analyses, to the appropriate analysis visit based on the EOS' actual study day (where Study Day 1 = day of first dose of study drug in this study).

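### By-visit safety tables pool early-withdrawal values with Week 84 values and leave out extremes found at unscheduled visits

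*SAP*

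**What the plan says.** - **Analysis visits for safety.** Section 7.5 lists the eCRF visits, one of which is Week 84/EOS, and says they "will be used as the analysis visits for analysis of most safety parameters including vital signs, laboratory examinations, and ECGs".
- **Meaning of EOS.** Section 7.2.6: "The end of study (EOS) is defined as date of early termination or the date of completion of treatment for enrolled patients". The EOS value is the last non-missing one up to that date.
- **The sponsor's own finding.** The Note to File of 23 November 2015, appended to the SAP, observes that the Week 84/EOS visit holds not only completers' Week 84 data "but also efficacy data assessed at the last visit (ie, EOS visit) for patients discontinued from the study prior to Week 84". It reassigns those records by actual study day for the EORTC questionnaires, the Subjective Global Assessment and plasma 5-HIAA. It names no safety parameter.
- **Unscheduled values.** Section 7.1: "extra measurements (such as unscheduled or repeat assessments) will not be included in summary tables unless specified otherwise". They go to the listings.
- **Safety displays.** Under Section 9.5, counts of outlying QTcF values "will be presented by study visit and treatment group". Section 9.3 plans a laboratory shift table across the analysis visits. Neither section mentions a worst or any-time post-Baseline summary.
- **Choosing among records.** Section 7.1: "the latest value at the visit will be used for summarization and analyses". Section 7.5: "the record closest to the planned assessment day will be selected for analysis", with the later record taken on a tie. Section 9.4 averages multiple vital-sign measurements.

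**The concern.** Long-term safety is the primary objective (Section 3.1), and Section 9 evaluates it by descriptive tables and listings. Two features weaken the by-visit tables.

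First, the last column is neither a Week 84 summary nor a clean last-value summary. It combines a fixed time point with a floating one, and a reader cannot separate them. The sponsor saw this problem and repaired it for the secondary (efficacy) data only.

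Second, QTcF outlier counts and laboratory shifts exist to show extremes, yet as written they draw only on scheduled visits. An extreme found between visits is not counted in the table meant to show it.

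A smaller matter adds to this: two rules for choosing among records can give different answers for the same laboratory or ECG visit.

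**Working it through.** The plan states no figure to reproduce. The check sets the sections side by side and adds day arithmetic.

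**1. One visit, two labels.** Week 84 is 84 × 7 = Day 588. The note's 12-weekly windows (Subjective Global Assessment and 5-HIAA) assign Day 42 to 125 to Week 12 and Day 546 to 588 to Week 84. Suppose a patient has an EOS visit at Day 70:
- 5-HIAA: Day 70 lies in 42 to 125, so it is Week 12.
- Laboratory value or QTcF: the eCRF label stands, so it is Week 84/EOS.

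The gap between actual day and Day 588, for EOS records that the note would move away from Week 84, is:
- at Day 42: 588 − 42 = 546 days = 78 weeks;
- at Day 545: 588 − 545 = 43 days = 6.1 weeks.

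EOS records before Day 42 fall in none of the note's windows and have a larger gap still.

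**2. Which measurements are most exposed.** Table 1 schedules ECG, urinalysis and chromogranin A on treatment only at Day 1, Week 48 and Week 84/EOS. A patient who leaves before Week 48 therefore contributes a scheduled post-Baseline on-treatment value only to the combined column.

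**3. How mixed the column could be.** The SAP gives no dropout rate, no EOS attendance and no withdrawal times, so these are assumptions. With a fraction d withdrawing early, a fraction a of those attending EOS, and everyone else completing, the early share is d·a / (d·a + 1 − d). If all attend and exit days are spread evenly over Day 42 to 545 (mean (42 + 545)/2 = 293.5), the mean actual day in the column is 293.5·d + 588·(1 − d).

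| d | Share, all attend | Share, half attend | Mean actual time, all attend |
|---|---|---|---|
| 10% | 10% | 5% | Day 558.6 (week 79.8) |
| 30% | 30% | 18% | Day 499.7 (week 71.4) |
| 50% | 50% | 33% | Day 440.8 (week 63.0) |

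At an interim cut the share is probably higher. The Note to File of 3 November 2015 says many patients in the open-label studies were still on treatment, so fewer would have reached Week 84.

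**4. Unscheduled extremes.** The Section 7.1 exclusion applies unless something else is specified. Sections 9.3 and 9.5 specify nothing else for unscheduled records, and their displays are by visit. So a QTcF above 500 msec seen only at an unscheduled visit enters no row of the outlier table, and a laboratory value seen only there enters no shift table.

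**5. Record selection.** Take Week 48, planned Day 336, with a tolerance of ±5 days (Table 1). Suppose that visit has records at Day 334 and Day 340. The Section 7.1 rule takes Day 340. The Section 7.5 rule takes Day 334, since |334 − 336| = 2 is less than |340 − 336| = 4. Neither rule looks for the worst value.

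**The case against.** The strongest reply is that the column heading includes EOS, and EOS is defined, so the mixture is visible. Pooling last values under such a heading is a defensible descriptive choice. Efficacy differs: its visit labels enter a mixed model with a p-value per visit, whereas safety has no visit-based test. TEAE incidence, the first safety measure, is not tabulated by visit and is untouched. All of this stands and lowers the severity. It does not make the column readable as either a Week 84 result or a last-value result.

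A reader might infer that an extreme QTcF or laboratory value would appear nowhere. The documents do not support that. All safety data are listed, out-of-range laboratory values are flagged in the listings, an important abnormality can also enter the TEAE tables, and a DSMB reviews safety quarterly. The exclusion is a default, and the table shells (Attachment 1) are not shown, so a suitable row may exist there. What stands is that the SAP text plans no such row.

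A reader might also infer that ECGs end with Week 84/EOS. Table 1 adds a Follow-up ECG when the EOS ECG is abnormal, though that falls after study drug has stopped.

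Finally, the two selection rules can be read as having different scopes: repeats at one visit, and several records in one window. Even so, the SAP does not say which governs when both apply.

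**Conclusion.** The point holds for the by-visit laboratory, vital-sign and ECG summaries. As written, the Week 84/EOS safety column pools values from different times, and the same EOS visit can carry different visit labels in efficacy and safety tables. Laboratory shift and QTcF outlier tables can miss an extreme found at an unscheduled visit, and the selection rules for laboratory and ECG records are not reconciled.

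The textual defect rests on no assumption, but its size does. The shares of about 5% to 50% follow from assumed dropout and attendance, and should not be quoted as estimates for this trial. A reader might go further and conclude that the primary safety assessment is invalid. The documents do not support that, because TEAE summaries and full listings are unaffected. This is a should-fix.

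**What to change.** 1. **Week 84 column.** Restrict it, for safety data, to values from Day 546 onward. Show all patients' EOS values in a separate last on-treatment value row. For laboratory tests and vital signs, early EOS values may also be mapped by actual study day with the note's 12-weekly windows, leaving values before Day 42 only in the last-value and worst-value rows. For ECG, urinalysis and chromogranin A, use the separate row or windows built on their own schedule. The 12-weekly windows would scatter these values into visits at which nobody is due to be measured.
2. **Extremes.** Add worst post-Baseline rows to the laboratory shift tables and any post-Baseline rows to the QTcF outlier table. Both should include unscheduled, repeat and EOS records.
3. **One selection rule.** For by-visit summaries, keep the record closest to the target day, the later one if tied. Name the Section 9.4 average for vital signs as the exception, and delete the latest-value sentence in Section 7.1.

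The cost is an extension of the existing note, a few more table rows and a smaller n at Week 84. No new data are needed.

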7.6 POOLING OF CENTERS

Study sites will be pooled by country. Countries may be pooled by region if necessary to support the proposed methods of analysis, as specified in [Section 8](#).

8 PLANNED ANALYSES

8.1 PATIENT DISPOSITION AND WITHDRAWALS

Disposition will be summarized for all enrolled patients. The number and percentage of patients who complete or discontinue prematurely from the study will be summarized

1003157

Lexicon Pharmaceuticals, Inc.

LX1606.302

Final V1.0

Statistical Analysis Plan

by treatment group and overall. In addition, the number and percentage of patients who discontinue from the study will be summarized by reason for discontinuation.

The number and percentage of patients included in each analysis population (SAF and PP) will be summarized by treatment group. The number of patients enrolled from each parent study will also be summarized.

A listing of disposition will be provided for all patients. The start and stop dates for each patient will be listed.

8.2 PROTOCOL DEVIATIONS

Protocol deviations will be captured during monitoring visits. Before database lock, the study Sponsor will review all protocol deviations and determine whether or not they are significant protocol deviations. Additional deviations may be identified through programmatic check or during clinical review of the data.

Significant protocol deviations include, but are not limited to, the following:

- Patient did not meet all inclusion or met any of the exclusion criteria
- Patient's study drug compliance rate was <75%

All significant protocol deviations by treatment group will be listed.

8.3 DEMOGRAPHIC AND OTHER BASELINE CHARACTERISTICS

Demographics and baseline characteristics will be listed and summarized by treatment group and overall for all patients in the SAF. Demographic characteristics will include age, sex, race, ethnicity, country, and region. Baseline characteristics summarized will include childbearing potential status. Age will be categorized as <65 years or ≥65 years.

All information including inclusion/exclusion criteria and pregnancy test(s) will be listed.

8.4 MEDICAL HISTORY

Medical history will be coded using the Medical Dictionary for Regulatory Activities (MedDRA) coding dictionary version 15.1. The version of the coding dictionary used will be included in a footnote on the output. Coded medical history terms will be summarized for the safety population by treatment group, MedDRA system organ class (SOC), and preferred term (PT). SOC terms will be sorted alphabetically and then PT will be sorted in order of frequency of the total column within each SOC.

1003157

Lexicon Pharmaceuticals, Inc.

LX1606.302

Final V1.0

Statistical Analysis Plan

Patient listings of coded medical history terms will be provided.

8.5 MEDICATIONS AND PROCEDURES

Medications (prior, concomitant) will be coded based on the World Health Organization Drug dictionary, version September 2012. The version number will be included in a footnote on the output. Medications will be summarized by presenting the frequency and percentage of patients using medications for each treatment group for the SAF based on Anatomical Therapeutic Chemical (ATC) Level 2 and the PT. Medications will be sorted alphabetically and patients will be counted only once for each medication class and each PT.

For patient listings, medications will be reported based on therapeutic subgroup (ATC Level 2) and PT; multiple medications for an individual patient will be listed by start date and then by stop date, from earliest to latest medications.

8.5.1 Prior Medications

All medications and other treatments taken by patients within 30 days prior to the Day 1 visit will be recorded on the eCRF. Prior medications are defined as medications taken prior to the first dose of telotristat etiprate. Partial date imputation for medications is described in [Section 7.4](#).

Prior medication use will be summarized by level 2 ATC and PT using the number and percentage of patients by treatment group. Medications will be sorted alphabetically by ATC and preferred name within ATC. Patients with multiple occurrences of a medication in ATC and preferred name will only be counted once within each ATC and preferred name.

8.5.2 Concomitant Medications

Concomitant medications are defined as medications that are taken on or after the first dose date of telotristat etiprate. Partial date imputation for medications is described in [Section 7.4](#). Concomitant medications will be summarized for the SAF by level 2 ATC and PT.

8.5.3 Treatment Compliance

Patients will be instructed to take telotristat etiprate tablets tid during the treatment period. Treatment compliance, as a percentage, will be calculated as $\text{Compliance} = \frac{\text{actual doses taken in tablets}}{\text{expected doses in tablets}} \times 100$. The treatment compliance is recorded on the eCRF.

1003157

Lexicon Pharmaceuticals, Inc.

LX1606.302

Final V1.0

Statistical Analysis Plan

Patients will be considered compliant overall for telotristat etiprate if the compliance is $\geq 75\%$. Descriptive statistics (number of patients, mean, SD, minimum, median, and maximum) for treatment compliance will be summarized by treatment group and overall for the safety population. In addition, treatment compliance will be categorized as $< 75\%$, $75\% - 125\%$, or $> 125\%$.

8.5.4 Concomitant Procedures

Concomitant procedures are defined as procedures that are conducted on or after the first dose date of telotristat etiprate. Disease progression is also recorded under concomitant procedures. All data will be presented by patient listing.

8.6 EFFICACY

Analyses of the efficacy data will be performed on the PP population, and the analysis will be applied to the QoL measures, adequate relief of CS symptoms, subjective global assessment, and plasma 5-HIAA values. Majority of patients enrolled in this study may have progressive disease, and their symptoms (not governed by inhibition of serotonin synthesis) may get worse due to disease progression.

The primary analysis will be based on the observed data and missing data will not be imputed, unless stated otherwise for specific analyses. All efficacy and pharmacodynamic variables (plasma 5-HIAA) will be summarized descriptively per study visit as the actual outcomes and change from Baseline scores where applicable, and listed.

Statistical tests and estimates of within patient effects for these measures will be derived from application of a mixed model with repeated measures (MMRM). The model will be generalized to handle missing data and specific to the measurement properties of the dependent variables. Non-parametric methods will be used to supplement the tests and estimates from the mixed linear model. Analysis of efficacy endpoints will be made using statistical tests each with a 2-sided α -level = 0.05.

8.6.1 Change from Baseline in Overall and Domain Scores of the EORTC QLQ-C30 and GI.NET21 at Each Study Visit

The EORTC QLQ is an integrated system for assessing the health related QoL of cancer patients participating in international clinical trials. The QLQ-C30^[2] version 3.0 is composed of both multi-item scales and single-item measures. These include 5 functional scales (physical functioning, role functioning, emotional functioning, cognitive functioning, and social functioning), 3 symptom scales (fatigue, nausea and vomiting, and pain), a global health status / QoL scale, and 6 single items (dyspnea, insomnia, appetite loss, constipation, diarrhea, and financial difficulties). All of the

Statistical Analysis Plan

scales and single-item measures range in score from 0 to 100. A high scale score represents a higher response level.

For all scales, the *RawScore*, *RS*, is the mean of the component items:

$$RawScore = RS = (I_1 + I_2 + \dots + I_n) / n$$

Then for functional scales:

$$Score = \left\{ 1 - \frac{RS - 1}{range} \right\} \times 100$$

And for symptom scales / items and global health status /QoL:

$$Score = \{(RS - 1) / range\} \times 100$$

Missing data rules will be applied such that the scale/item scores will be computed based on the non-missing item responses, as long as at least half of the items in the scale had non-missing values. If responses to more than half of the items in the scale are missing, the scale score will be recorded as missing.

Table 2: Items and Scale Structure of QLQ-C30

	Number of Items	Item Range	Item Numbers
Global health status/QoL	2	6	29, 30
Functional scales			
Physical functioning	5	3	1 to 5
Role functioning	2	3	6, 7
Emotional functioning	4	3	21 to 24
Cognitive functioning	2	3	20, 25
Social functioning	2	3	26, 27
Symptom scales / items			
Fatigue	3	3	10, 12, 18

Statistical Analysis Plan

Nausea and vomiting	2	3	14, 15
Pain	2	3	9, 19
Dyspnea	1	3	8
Insomnia	1	3	11
Appetite loss	1	3	13
Constipation	1	3	16
Diarrhea	1	3	17
Financial difficulties	1	3	28

The GI.NET21^[3] module for patients with gastrointestinal-related neuroendocrine tumors includes 21 items, conceptualized as consisting of 5 scales and 4 single items.

The scoring algorithm for the GI.NET 21 scales and single items follows the same rule as the EORTC QLQ-C30 functional scales calculation.

Table 3: Items and Scale Structure of GI.NET21

	Number of Items	Item Range	Item Numbers
Scales			
Endocrine scale	3	3	31, 32, 33
Gastrointestinal symptoms scale	5	3	34, 35, 36, 37, 38
Treatment scale	3	3	39, 40, 46
Social function scale	3	3	42, 44, 49
Disease related worries scale	3	3	41, 43, 47
Single Items			
Muscle /bone pain symptom	1	3	48
Sexual function	1	3	51
Information/communication function	1	3	50
Body image	1	3	45

1003157

Lexicon Pharmaceuticals, Inc.

LX1606.302

Final V1.0

Statistical Analysis Plan

The change from Baseline in overall and each domain score of EORTC QLQ-C30 and GI.NET21 at each study visit will be analyzed using a MMRM for the PP population. The model will use the change from Baseline in overall or each domain score of EORTC QLQ-C30/GI.NET21 as the dependent variable and will include a fixed effect of time (Baseline Day 1 up to Week 84/EOS). The Baseline QLQ-C30/GI.NET21 value will be included in the model as a covariate. The Kenward-Roger approximation will be used to adjust the denominator degrees of freedom. A first-order heterogeneous autoregressive covariance structure will be assumed initially to model the within-patient errors; however, other covariance structures will be tested and may be used in the final model if a better fit is evident. The least squares (LS) means, 95% 2-sided CLs, and the p-values of LS means at each visit will be reported to evaluate the within-patient treatment effect. The null hypothesis is that there is no treatment effect (no difference from Baseline values) over time. A sample SAS code for the model is shown below.

*USUBJID: unique patient ID
AVISITN: analysis visit (e.g., week 24, week48, week 72 and week 84)
RESP: non-count data (e.g., change from Baseline in Global health status/QOL score)
BASE: non-count data (e.g., Baseline Global health status/QOL score);

```
ods output lsmeans=estimates;  
proc mixed data=adeft method=reml;  
  class USUBJID AVISITN;  
  model RESP = AVISITN BASE / ddfm=kr;  
  repeated AVISITN / subject=USUBJID type=ARH(1);  
  random intercept / subject=USUBJID;  
  lsmeans TRT01PN*AVISITN / cl;  
run;  
ods output close;
```

Friedman's nonparametric method for testing treatment group differences will be used to supplement the MMRM. Friedman's test uses the ranks of the data rather than their raw values to calculate the statistic, and the test does not make a distribution assumption of the data. The null hypothesis of the test is that the change from Baseline in Global health status/QOL score are the same over time, and the alternative hypothesis is that the change from Baseline in Global health status/QOL score are different over time. Friedman's test cannot handle missing data, so patients with incomplete measurements will be dropped when applying Friedman's test. A sample SAS code for the model is shown below.

*USUBJID: unique patient ID
AVISITN: analysis visit (eg, week 24, week48, week 72 and week 84)
RESP: change from Baseline in Global health status/QOL score;

```
proc freq data=adeft;
```

Lexicon Pharmaceuticals, Inc.
[name]
[name]

1003157

Lexicon Pharmaceuticals, Inc.

LX1606.302

Final V1.0

Statistical Analysis Plan

```
tables USUBJID*AVISITN*RESP / cmh2 scores=rank noprint;  
output out = FriedRes (keep=group p_cmhrms) cmh2;  
run;
```

A graphic display of the change from Baseline value and its 95% CLs over time for each treatment group will be provided.

